18.3. Device deficiency

A device deficiency is the inadequacy of the investigational medical device or comparator with respect to its identity, quality, durability, reliability, usability, safety, or performance. This includes malfunctions, use errors and inadequacy in the information supplied by the manufacturer including labelling.

18.4. Serious adverse events (SAE)

A serious adverse event is an adverse event that:

Led to death,

- Led to a serious deterioration in the health of the subject, users or other persons as defined by one or more of the following:
 - 1) a life-threatening illness or injury, or
 - a permanent impairment of a body structure or a body function including chronic diseases, or
 - 3) in-patient or prolonged hospitalization, or
 - 4) medical or surgical intervention to prevent life-threatening illness or injury or permanent impairment to a body structure or a body function.
- Led to foetal distress, foetal death, a congenital abnormality, or birth defect including physical or mental impairment.

This includes device deficiencies that might have led to a serious adverse event if:

- 1) Suitable action had not been taken, or
- 2) Intervention had not been made, or
- 3) Circumstances had been less fortunate.

These are handled under the serious adverse event reporting.

Planned hospitalization for a pre-existing condition, or a procedure required by the CIP, without serious deterioration in health, is not considered a serious adverse event.

18.4.1. Serious adverse device effect (SADE)

A serious adverse device effect is an adverse device effect that has resulted in any of the consequences characteristic of a serious adverse event.

18.4.2. Anticipated serious adverse device effect (ASADE)

Anticipated serious adverse device effect is any effect that by its nature, incidence, severity, or outcome has been previously identified in the risk analysis report.

18.4.3. Unanticipated serious adverse device effect (USADE)

An unanticipated serious adverse device effect is a serious adverse device effect which by its nature, incidence, severity, or outcome has not been identified in the current version of the risk analysis report.

Reporting in the eCRF of any ADE, SADE and/or DD of the investigational test product Biatain® Silicone will be reported by the Clinical Manager to Vigilance.

18.5. Medical care of subjects

Principal investigator shall ensure that adequate medical care is provided to a subject experiencing an adverse event during and after participation in the clinical investigation. All serious adverse events will be followed until a resolution is addressed.

The current status of all ongoing adverse events is documented during site close-out.

Principal Investigator or delegate shall provide the subject with the necessary instructions on proper use, handling, storage and return of the test products, when it is used or operated by the subject.

18.6. Reporting and timelines

All adverse events and device deficiencies will be reported in the eCRF. If, for some reason, the system is off-line, investigators (or designee) are required to report the event to:

[contact]

18.7. Investigator's reporting responsibilities

PI at each site must assess all (S)AE's that occur at his/her site.

- All serious adverse events and serious adverse device effects must be reported to sponsor within 24 hours of the site becoming aware of the event.
- A device deficiency that could have led to a serious adverse event but did not because suitable
 action was taken, intervention had been made or because of fortunate circumstances should
 be reported to sponsor within 24 hours of the site becoming aware of the event.
- New findings and/or updates in relation to already reported serious events should also be reported to sponsor within 24 hours of the site becoming aware of the event.
- Device deficiencies and all adverse device effects related to CE marked Coloplast investigational product and/or comparator must be reported to sponsor within 24 hours of becoming aware of the event.

When reporting the SAE, the relationship to the test material shall be described whether the event is considered:

- Not related, the event has no temporal relationship with the use of the test material or the
- procedures.
- Unlikely related, the relationship with the use of the test material seems not relevant and/or
 the event can be reasonably explained by another cause, but additional information may be
 obtained.
- Possible related, the relationship with the use of the test material is weak but cannot be ruled
 out completely. Alternative causes are also possible (e.g., an underlying or concurrent illness/
 clinical condition or/and an effect of another device, drug, or treatment). Cases where
 relatedness cannot be assessed, or no information has been obtained should also be
 classified as possible.
- Probably related, the relationship with the use of the test material seems relevant and/or the
 event cannot reasonably be explained by another cause, but additional information may be
 obtained.
- **Definitely related/Causal relationship,** the event has a temporal relationship with the test material use/application or procedures.

The investigator will assess intensity for each AE and SAE reported during the investigation and assign it to one of the following categories:

- Mild, the intensity of the event is mild with no further action or intervention
- Moderate, the intensity of the event will lead to an action or intervention to solve the event
- **Severe,** the intensity of the event will lead to follow up on the action or intervention, as the effect of the action or intervention may not decrease the symptoms.

All above events must be reported by use of the relevant adverse event/serious adverse event/device deficiency form.

Please report to:

Coloplast A/S [name]

[contact]

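### The adverse-event intensity grades in section 18.7 mix intensity with handling: a trivial treated event cannot be Mild, and an intense event needing no action fits no grade

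*Combined protocol and SAP*

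**What the plan says.** Section 18.7 makes the grade compulsory: "The investigator will assess intensity for each AE and SAE reported during the investigation". It then sets out three grades.

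- The lowest grade, Mild, is worded as "the intensity of the event is mild with no further action or intervention", which sets two conditions at once.
- The middle grade, Moderate, is for use when "the intensity of the event will lead to an action or intervention to solve the event"; no level of symptoms is given.
- For the highest grade, Severe, the criterion is that "the intensity of the event will lead to follow up on the action or intervention". The reason attached to it reads "as the effect of the action or intervention may not decrease the symptoms".

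Section 18.1 names the same three labels without defining them. No other section gives a scale based on symptoms or impairment. Section 18.2 uses the word intensity in its ordinary sense, when it says that irritation on dressing removal counts as a device effect only if its intensity or duration is abnormal.

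On use, section 10.1 has adverse events listed and, where relevant, summarised. It specifies no analysis by intensity.

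**The concern.** An intensity scale should place every event in exactly one grade, and the grade should depend on how bad the event was for the subject. This scale does neither reliably. Mild joins two conditions, one on intensity and one on handling. Moderate and Severe are told apart only by what the intensity leads to, an action or follow-up of that action. Two subjects with the same symptoms can therefore be graded differently because one site acted and the other did not.

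The trial is open-label (section 5.9) and runs at more than 12 UK sites (section 5.1), so the choice to act lies with staff who know the allocation and who may differ in habit. Barrier cream is the plan's own example of an extra product used in standard care (sections 5.6 and 7.5), so a minor skin reaction can easily attract an action. At stake is the meaning of the intensity column in the safety listing and summary, which feed a report that goes to the ethics committee and regulators (section 20).

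**Working it through.** No formula applies to the definitions, and the plan gives no figure to reproduce. The check is a literal reading of the section 18.7 wording.

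**Step 1: conditions for each grade.**

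- Mild = mild intensity AND no action.
- Moderate = the intensity leads to an action.
- Severe = the intensity leads to follow-up of an action AND the reason is that the action may not relieve symptoms.

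**Step 2: apply them to two intensities by three kinds of handling.**

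| | No action | Action that settles it | Action, then follow-up because relief is doubtful |
|---|---|---|---|
| Trivial | Mild | Moderate | Severe |
| Intense | no grade | Moderate | Severe |

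**Step 3: count.** Of 2 × 3 = 6 cells, 1 has no grade (intense, no action): Mild fails on intensity, and Moderate and Severe fail because there is no action. In 2 of 6 cells a trivial event is graded above Mild. In the two right-hand columns the grade is the same for trivial and intense events, so there it follows handling alone. An example of the trivial, treated cell is slight maceration given barrier cream, which cannot be Mild and becomes Moderate.

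These are counts of logical cases. They do not estimate how many subjects would be affected, and the documents do not allow that number to be derived.

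**Step 4: how common the local reactions might be.** Table 5 (section 18.2) gives rates for six anticipated device effects: 0.13 + 0.09 + 0.09 + 0 + 0 + 0.09 = 0.40%. The denominator is not stated. Assume 50 test-arm subjects (half of 100).

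- If the rate is per subject: 50 × 0.0040 = 0.2 events.
- If it is per product, at the section 4.7 maximum of 12 each: 50 × 12 × 0.0040 = 2.4 events.

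Table 5 covers anticipated device effects only. The scale applies to all adverse events, so these figures understate the number of events graded.

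**Step 5: what depends on the grade.** Expedited reporting in sections 18.7 and 18.8 turns on seriousness, device-relatedness and device deficiencies. The pass/fail criterion in section 10.4 rests on wound area and cost. The sample size in section 10.2 rests on the standard deviation of wound area reduction. None of these uses the intensity grade.

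**The case against.** The strongest reply is that the definitions are worded around intensity throughout. Mild says so outright, and the other two ask what the intensity will lead to, not whether an action happened to be taken. That is right, and a reader who infers that the scale ignores intensity altogether goes too far: the empty cell exists only because Mild contains an intensity condition. The reply does not rescue the scale. If a trivial event is treated out of habit and its intensity is held not to have led to the action, it still fails Mild, and it then fits no grade.

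Four stronger readings are tempting, and the documents do not support them.

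- *Weekly visits push treated events to Severe.* The visits are scheduled for every subject (section 5.1). A routine re-check is not follow-up prompted by the event's intensity, and Severe also needs doubt about relief.
- *Every treated serious event becomes Severe.* Section 18.5 says "All serious adverse events will be followed until a resolution is addressed", but that follow-up is triggered by seriousness, not by intensity.
- *Treated local reactions will pile up in the upper grades.* The Table 5 rates suggest few such events in this trial. Section 18.2 also takes temporary irritation at dressing removal out of the device-effect definition, though not expressly out of the adverse-event definition.
- *The test arm will look worse because staff act sooner on an unfamiliar product.* Nothing says that the product is unfamiliar. It has been CE-marked since 2013 (section 4.1) and staff are trained in its use (section 4.6). An open-label assessor could colour any scale.

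It is also fair to say that seriousness is defined separately (section 18.4), so intensity is not the only indication of how grave an event was. Additional wound-care products and changes of dressing are already recorded at visits (section 7.2). The event form itself is not in the documents, so it may already have a field for action taken.

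What stands after all this is the mixture of two concepts, the absence of a symptom criterion in Moderate and Severe, and the gap.

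**Conclusion.** The point holds as a minor defect in a data-collection definition. Section 18.7 requires a grade for every event and supplies a scale that cannot grade an intense event needing no action, and that cannot call a trivial treated event Mild. The conclusion rests on a literal reading of the three definitions and on there being no symptom-based scale elsewhere in the document. Training material or the event form might supply one, but neither is available here.

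The effect stays within the adverse-event listing and any summary by intensity. That the grade partly reflects site handling follows from the wording. That this would favour or harm either arm is not shown.

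**What to change.** In section 18.7, define all three grades by symptom level or by effect on the subject. For example: Mild, noticed without interfering with usual activities; Moderate, interferes with them; Severe, prevents them. Refer to that definition from section 18.1. Keep action taken and follow-up as separate items on the adverse-event form, if it does not already have them, so that nothing the present wording captures is lost.

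The cost is a wording change to section 18.7 and the form, and a line of site training. The change would be logged under section 12; that section gives assessment methods as an example of a significant change, so the sponsor should check whether ethics committee notification is needed. No extra visits or data sources are required.

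One drawback is that interference with activities may discriminate less well here, because section 5.1 notes that many wound-care patients have reduced mobility. Wording based on symptom level would avoid this for local skin reactions and would close the gap equally well.

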18.8. Sponsors reporting responsibilities

It is the responsibility of sponsor to ensure that the following are reported to national regulatory authorities and EC, as applicable, immediately, but no later than 7 calendar days following the date of awareness by sponsor.

- All serious adverse events.
- All serious device effects.
- All device deficiencies that could have led to serious adverse events but did not because suitable action was taken; intervention had been made or because of fortunate circumstances.
- New findings and/or updates in relation to already reported events.

If the serious adverse event results in imminent risk of death, serious injury, or serious illness that requires prompt remedial action for other subjects, users or other persons or a new finding to such a serious adverse event, sponsor must immediately but no later than 2 calendar days after awareness by sponsor report the event to national regulatory authorities and ethics committees, as applicable.

It is the responsibility of sponsor to inform all investigators in writing within 10 working days if device deficiencies, adverse events, adverse device effects, near-incidents, serious adverse events, serious adverse device effects or unanticipated serious adverse device effects lead to corrective actions (e.g., change of IFU).

19. Suspension or premature termination of the clinical investigation

Sponsor may suspend or prematurely terminate an investigation site or the entire clinical investigation for documented significant reasons.

If a suspicion of an unacceptable risk to subjects develops during the clinical investigation, sponsor will suspend the investigation while the risk is assessed. Sponsor will terminate the investigation if an unacceptable risk is confirmed. Sponsor will ensure that the premature termination will be justified in writing and will promptly inform the regulatory authorities and relevant EC(s). If monitoring or auditing of the clinical investigation identifies serious or repeated deviations at one of the participating investigation sites, sponsor will suspend or terminate the particular investigational site. The sponsor or investigator will inform the regulatory authority as appropriate and notify the EC about the termination of the site.

If suspension or termination of the clinical investigation occurs, the investigator will promptly inform the enrolled subjects. Sponsor will provide resources to fulfil the obligations from the CIP for follow-up of the subjects as necessary.

20. Clinical investigation report

At completion of the investigation sponsor is responsible for writing the clinical investigation report. The report is retained on file. The report contains a critical evaluation of all data, which have been collected during the investigation. The report describes the methodology and design and a data analysis, including statistical preparation and conclusion.

Sponsor and coordinating investigator must sign the final version of the clinical investigation report or an affidavit, indicating their agreement with the contents. If no coordinating investigator is appointed, then the signatures of the principal investigator(s) should be obtained.

The clinical investigation report must be submitted to EC and regulatory authorities.

21. Publication policy

Coloplast, sponsor, is referring to the internal document 'Clinical Publication Policy' that will be available for internal and external persons involved in the publication process.

The investigation will be registered in a publicly accessible database before recruitment of the first subject. The results of the investigation, positive as well as inconclusive and negative will be published in the same publicly accessible database. The subjects' identity will remain confidential. Publication of results in the database will be conducted per the law of personal data protection and will be initiated as soon as scientifically acceptable, however, within one year after the last subject has completed the investigation. Data from the investigation is considered confidential until it is published per the conditions of this Clinical Investigation Plan and the 'Clinical Publication Policy'. Sponsor may publish anonymous single subject case stories (or public, if the subject consents) at any time during and after the investigation. The identification of the participant must not be possible. Sponsor reserves the right to use the data (published and unpublished) for reimbursement or regulatory purposes.

- may be used on patients who are in treatment for a local or systemic infection at the discretion of a health care professional is suitable for use in combination with compression theraps

The product consists of:

- a vapour permeable top film which is bacteria- and waterproof a lock away layer
- an absorbent polyurethane foam a perforated silicone adhesive
- burguoise protective films

If for experience a suspected allergic reaction or any other side effects, please contact four health care professional.

Sterilised using eth/lene oxide (EO).

Coloplast accepts no liability for any injury or loss that may arise if this product is used in a manner contrary to Coloplastis current

Special storage conditions Keep away from sunlight.

How to use

Preparation

Cleanse the wound and periwound skin in accordance with local guidelines, e.g. lukewarm water or physiological saline solution.

Gently dry the periwound skin.

If any film, cream, cintment or similar product is used, allow the periwound skin to dry before applying the product.

Select a product where the foam overlaps the wound edge by approximately 1-2 centimetres.

Open the pouch and pick up the product from the packaging.

Use the protective films to avoid touching the adhesive side and to ensure aseptic application.

Remove the center protective film.

[figure not shown]

Apply the achesive side towards the wound.

Remove the remaining protective films, one at a time.

Gently run your fingers around the edge of the product to ensure an even and smooth fit to the skin.

Instructions for use

Please read the following instructions carefully.

IFU Master Biatain Silicone Version 2

The Coloplast logo is a registered trademark of Coloplast A/S. All rights reserved.® 2021-08-31

Intended purpose

The product is intended for moist wound healing and exudate management.

The product is intended to be used by health care professionals and patients under the supervision of health care professionals.

Indications

- is indicated for a wide range of low to highly exuding wounds. This includes acute wounds such as donor sites, post operative wounds and traumatic wounds; and chronic wounds such as leg uicers, pressure ulcers and non-infected diabetic foot ulcers may be used to prevent post-operative blistering.

Warnings

Do not re-use the single use product as cross contamination may occur, potentially leading to infection.

Reprocessing, washing, disinfection and/or resterilisation may compromise product characteristics, causing additional risk of physical harm or infection to the user.

A health care professional should frequently inspect and manage infected wounds, diabetic wounds and wounds which are solely or partially caused by arterial insufficiency, in accordance with local guidelines.

Do not use the product with oxidising salutions e.g. hypochlorite and hydrogen peroxide salutions, as this may cause product degeneration which may lead to deterioration of the wound. Ensure that any other evaporating solution is completely dried off before applying the product.

Do not cut the foam part of the product as this may lead to wound deterioration due to product residues left in the wound.

Do not use if package is damaged, as sterifty of the product may have been compromised, potentially leading to infection.

Keep away from surlight as it may impact product performance which may lead to maceration.

The product should be changed when clinical indicated, when visible signs of exudate approach the edge of the foam or after 7 days.

Loosen the adhesive border before gently lifting the product away from the wound and removing the product. If the product is difficult to remove, it should be maistened with water or physiological saline solution until it removes easily.

Disposal

The product is intended for single use only and should be disposed of in accordance with local guidelines, e.g. with normal household weste.

Do not flush the product down the toilet.

Reporting of incidents

If, during the use of this device or as a result of its use, a serious incident has occurred, please report it to the manufacturer and to four national authority.

Explanation of symbols

MD	Medic

Indicates that the product is in compliance with European legislation for medical devices

Catalogue number

Use-by date (YYYY-MM-DD)

Batch code

Date of manufacture (YYYY-MM-DD)

Manufacturer

Consult instructions for use

Do not re-use

Sterilised using ethylene coide

Single sterile barrier søstern

Not made with natural rubber latex

Do not use if package is demaged and consult instructions for use

Indicates a carrier that contains Unique Device Identifier ומיט

GTIN Global Trade Item Number

Keep away from sunlight

Recf clable packaging

♠ ♠ ♠ ♠ Absorption capability

Appendix 2: Instruction for Use Mepilex® Border

(14)

Mepilex® Border EM

Self-adherent soft silicone foam dressing

Do not reuse. If reused performance of the product may deteriorate, cross contamination may occur.

Sterile. Do not use if sterile barrier is damaged or opened prior to use. Do not re-sterilise.

Product description

Mepilex Border EM is a self-adherent, absorbent dressing that maintains a moist wound environment. The waterproof outer layer protects the wound from dirt and bacteria. The dressing has a Safetac® wound contact layer that is a unique adhesive technology. It minimises pain to patients and trauma to wound and skin at dressing removal.

Mepilex Border EM consists of:

- a wound contact layer consisting of soft silicone adhesive (Safetac) and a film carrier
- a flexible absorbent pad in two layers: a foam and a non-woven spreading layer
- an outer film which is breathable but waterproof, providing a barrier to external contaminants

Dressing material content:

Silicone, polyurethane, polyacrylate, viscose, polyester and polyolefin.

Indications for use

Meplex Border EM is designed for the management of a wide range of non/low exuding wounds, such as leg and foot ulcers, pressure ulcers, surgical wounds and traumatic wounds e.g. abrasions, blisters and skin tears.

Mepilex Border EM can also be used as protection of compromised and/or fragile skin

Precautions

- Do not use on patient with known hypersensitivity to the dressing or its ingoing materials.
- Do not use together with oxidising agents such as hypochlorite solutions or hydrogen perceide.
- If you see signs of clinical infection e.g. fever or the wound or surrounding skin becoming red, warm or swollen, consult a health care professional for appropriate treatment.

Instructions for use

Mepilex Border EM may be used by lay persons under supervision of health care professionals.

- Cleanse the wound according to clinical practice. Dry the surrounding skin thoroughly.
- Select an appropriate dressing size/shape. The wound pad should cover the dry surrounding skin by at least 1-2cm.
- 3. Remove the lirst release film and apply the adherent side to the wound.
- 4. Remove the remaining release film(s) and smooth down the border on the skin.

 Do not stretch the dressing.

The dressing change interval may be several days. Change the dressing before it is fully saturated, at signs of leakage, or as indicated by clinical practice. Mepilex Border EM can be used under compression bandaging, and in combination with gels.

Special storage conditions and handling conditions

Mepilex Border EM should be stored in dry conditions

The foam may change colour to more yellow when exposed to light, air and/or heat. This has no influence on product properties.

Disposal should be handled according to local environmental procedures.

Other information

If any serious incident has occurred in relation to the use of Mepilex Border EM, it should be reported to Mölnlycke Health Care.

Mepilex* and Safetac* are registered trademarks of Mölnlycke Health Care AB.

